### **16.2.1 Serious adverse events**

The number and percentage of patients with serious TEAE will be presented by SOC and PT in descending order of frequency in the anakinra group for each flare and overall. The narratives will be presented in listings.

The number and percentage of patients with at least one pre-treatment SAE will be summarized in frequency tables by SOC and PT.

The number and percentage of patients with at least one SAE will be summarized in frequency tables separately by day of onset: Day 1 to Day 28 and after Day 28 for each flare and overall.

### **16.2.2 Adverse events leading to withdrawal**

The number and percentage of patients with TEAEs leading to study withdrawal will be presented by SOC and PT, in descending order of frequency in the anakinra group for each flare and overall.

The number and percentage of patients with TEAEs leading to drug withdrawal will be presented by SOC and PT, in descending order of frequency in the anakinra group for each flare and overall.

### **16.2.3 Deaths and other serious adverse events**

A summary of deaths and other serious adverse events will be presented in listings.

The narratives of deaths and other serious adverse events will also be presented in listings.

### **16.3 Laboratory data**

The presentations will be based on the results from the central laboratory safety data.

The laboratory safety data will be presented as actual values at baseline, 72 hours, Day 8 and Day 15 and changes from baseline at 72 hours, Day 8 and Day 15 for each flare by descriptive statistics.

The number and percentage of patients with low, normal, or high laboratory values at baseline versus 72 hours, Day 8 and Day 15 for the first flare will be presented using shift tables. For subsequent flares the number and percentage of patients with low, normal, or high laboratory values at baseline for the flare of interest versus Day 15 will be presented using shift tables.

The values at 72 hours, Day 8 and Day 15 versus baseline for the flare of interest for each laboratory parameter for each flare will be presented in a scatterplot. Side by side plots for anakinra (different symbols for 100 mg and 200 mg) and triamcinolone will be performed.

Treatment emergent abnormal laboratory values will be listed. Values that are normal or high at baseline for each flare and shift to low at the corresponding visit, or that are normal or low at baseline and shift to high at the corresponding visit.

### **16.4 Vital signs**

Vital signs (blood pressure, pulse rate and body temperature) will be presented as actual values at baseline, 72 hours, Day 8 and Day 15 for each flare by descriptive statistics.

Treatment emergent abnormal vital signs will be listed. Values that are normal or high at baseline for each flare and shift to low at the corresponding visit, or that are normal or low at baseline and shift to high at the corresponding visit will be listed. See Section 18.25 for definition of low, normal and high.

### **16.5 Electrocardiogram**

ECG results at baseline will be summarized for each flare by descriptive statistics.

### **16.6 Anti-drug antibodies**

See Section 18.25 for definitions regarding immunogenicity.

### **16.6.1 Presence of anti-drug antibodies**

The number and proportion of patients with presence of ADA (treatment induced, treatment boosted or treatment unaffected), NAb and cross-reactivity at baseline, Day 8, Day 15, Day 28 and Week 12 will be summarized for each flare.

For patients with presence of ADA, the ADA titers at baseline, Day 8, Day 15, Day 28 and Week 12 will be summarized by descriptive statistics for each flare. Depending on how the results are reported, ADA titers might be categorized as eg. low (<50), medium (>50 and <500) or high (>500).

The cumulative number and proportion of ADA positive and ADA negative subjects will also be summarized by flare over the study.

The number and proportion of transient ADA positive patients, persistent ADA positive patients and off-treatment persistent ADA positive patients will be summarized for the whole study,

The number of patients with occurrence of transient and persistent ADA during the study will be presented graphically.

### **16.6.2 Anti-drug antibodies versus safety**

AEs and SAEs will be presented by ADA positive and ADA negative patients for the whole study period by SOC and PT. ADA positive patients will then be further categorized in:

1. Transient ADA positive patients.
2. Persistent ADA positive patients.

SAEs will be listed together with the ADA titer for the positive ADA sample taken closest before and after the start of the event.

### **16.6.3 Anti-drug antibodies versus efficacy**

The mean pain intensity on VAS at each timepoint up to Day 8 will be presented by ADA presence and by NAb presence by descriptive statistics and in graphs as applicable. The presentations will be repeated for each subsequent flare. ADA presence will be defined as being ADA positive at least once at Day 1 or Day 8; no ADA presence will be defined as being negative at both Day 1 and Day 8. Undetermined ADA presence is defined as both assessments are missing or if one assessment is negative and the other is missing.

For subsequent flares, the ADA titer at Day 1 will be plotted against VAS at 72 hours.

For baseline, Day 8 and Day 15, CRP and SAA will be presented by ADA presence and by NAb presence. The presentations will be repeated for each subsequent flare. ADA presence will be defined as being ADA positive at least once at Day 1, Day 8 or Day 15; no ADA presence will be defined as being negative at both Day 1, Day 8 and Day 15. Undetermined ADA presence is defined as all assessments are missing or if 1 or 2 assessments are negative and the other assessments are missing.

For subsequent flares the ADA titer will be plotted against CRP and SAA at Day 1, Day 8 and Day 15.

#### **16.6.4 Anti-drug antibodies versus serum concentration of IL-1Ra/anakinra**

If ADA are present, the relationship between ADA and ADA titer and IL-Ra/anakinra concentrations over time will be explored, as applicable. Similarly the relation between presence of NAb and IL-Ra/anakinra concentrations over time will be explored.

## **17 Exploratory endpoints**

### **17.1 Short Form (36) Health Survey (SF-36)**

Based on the SF-36 questionnaire, the patient's score for each of the individual 8 domains as well as the PCS and the MCS will be calculated (see Section 18.27).

The change from baseline in SF-36 physical functioning domain score at Day 8 for the first flare will be evaluated using an analysis of covariance model including factors for treatment, ULT use (yes, no) and BMI ( $<30.0$ ,  $\geq 30.0$  kg/m^2), and baseline SF-36 physical functioning score as covariate. The estimated mean change in SF-36 physical functioning domain score for each treatment group (anakinra and triamcinolone), the estimated difference between the groups and the associated 95 % confidence interval and p-value from the model will be presented.

The patient's score and the change from baseline for the 8 domains as well as the PCS and the MCS at Day 8 and Day 15 will be presented by descriptive statistics.

For subsequent flares, the 8 domains from SF-36 as well as the PCS and the MCS at Day 8 and Day 15 will be presented by descriptive statistics.

### **17.2 EuroQol 5 dimensions 5 levels (EQ-5D-5L)**

The actual values and the changes from baseline in the 5 domains in EQ-5D, the EQ-5D-VAS and the EQ-5D Index at baseline, Day 8 and Day 15 for first and subsequent flares will be presented by descriptive statistics (see Section 18.28).

The EQ-5D Index value will also be presented by resolution of pain until Day 8 for the first flare.

In addition the distribution of categories in each EQ-5D domain will be presented at baseline and Day 8.

### **17.3 Work productivity and activity impairment:specific health problems (WPAI:SHP)**

Based on the WPAI:SHP the following scores will be calculated for Day 8 and Day 15; percent and actual work time missed due to gout, percent impairment while working due to gout, percent overall work impairment due to gout, percent activity impairment due to gout and in addition total work time will be calculated (see Section 18.29).

The WPAI:SHP scores at Day 8 and Day 15 for the first flare and subsequent flares will be presented by descriptive statistics.

### **17.4 Health care resource utilization**

The number of days with hospitalization and the number of unscheduled outpatient visits (Specialist, Nurse practitioner and GP/Family Physician) from Day 1 to Day 15 for the first flare and subsequent flares will be presented by descriptive statistics (see Section 18.30).

### **17.5 Exploratory inflammatory biomarkers**

The actual values at all timepoints and change from baseline in exploratory inflammatory biomarkers in serum (IL-6, IL-8, calprotectin, MPO and neopterin) at 72 hours, Day 15 and Week 12 (in case of no subsequent flare prior to the Week 12 time point) for the first flare and subsequent flares will be presented by descriptive statistics.

## **18 Derived and computed variables**

### **18.1 Unpermitted rescue medication**

Unpermitted rescue medication that leads to exclusion from PP population is defined as more than one incorrect intake, i.e. either type or outside time window (multiple incorrect intakes within 15 minutes is counted as one):

- Unpermitted type
  - Types other than paracetamol/acetaminophen and/or codein or tramadol or rescue medications classified as non-medicinal products (e.g. ice/cold pack, vinegar) and taken between treatment start and 72 hours.
  - Glucocorticoids (from general concomitant medication and rescue medication) taken between treatment start and 72 hours).
  - All unresolved OTHER <72 hours.

- Outside time window
  - All rescue (from rescue medication) taken prior to the 24 hours VAS pain assessment. If 24 hours VAS pain is missing, taken within 24 hours since treatment start.
  - All rescue (from rescue medication) taken within 6 hours prior to the 48 hours VAS pain assessment. If 48 hours VAS pain is missing, taken within 42 to 48 hours since treatment start.
  - All rescue (from rescue medication) taken within 6 hours prior to the 72 hours VAS pain assessment. If 72 hours VAS pain is missing, taken within 66 to 72 hours since treatment start.
  - All rescue (from rescue medication) with a missing timestamp (date and time) that can be related to a flare.

## 18.2 Age

Age will be calculated in full years without decimals, derived through the formula:  
 $\text{int}((\text{input}(\text{compress}(\text{RFSTDTC}, '-'), \text{best.}) - \text{input}(\text{compress}(\text{BRTHDTC}, '-'), \text{best.}))/10000)$ .  
 The method automatically corrects for leap days but is only correct for values without decimals.

## 18.3 Body mass index (BMI)

BMI will be calculated as:

$$\text{BMI} = \text{weight (kg)} / (\text{height (m)} * \text{height (m)})$$

## 18.4 Age at diagnosis of gouty arthritis

Age at diagnosis of gouty arthritis will be calculated in full years without decimals, derived through the formula:  $\text{int}((\text{input}(\text{compress}(\text{MHSTDTC}$  (where MHTERM = GOUTY ARTHRITIS), '-'), best.) -  $\text{input}(\text{compress}(\text{BRTHDTC}, '-'), \text{best.}))/10000)$ .

Since the date of diagnosis of gouty arthritis is only collected as month and year, the day will be imputed as the 15th, i.e. YYYY-MM-15, in the calculation. If the month is missing, it will be imputed as June, i.e. YYYY-06-15.

## 18.5 Disease duration

The disease duration (calculated in full years) is defined as:

- If the date of diagnosis is given only as a year: year of randomization - year of diagnosis.
- If the date of diagnosis is given as a year and a month:  $\text{INT}((\text{YYYYMM}_{\text{randomization}} - \text{YYYYMM}_{\text{diagnosis}})/100)$ .

## 18.6 Start of medical and surgical history

If the start date is missing, the medical and surgery history will be reported as started after randomization (first IMP injection).

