7.5.1.2 Pre-screening (optional)

Pre-screening is optional and may be done to identify patients that fulfil the study eligibility criteria with the exception of having a current flare of gouty arthritis.

When a pre-screened patient reports a flare of gouty arthritis, the procedures for the baseline visit (Visit 1) will be followed.

7.5.1.3 Baseline, Visit 1

A signed informed consent form must be obtained from the patient prior to any study-related activities. Once the ICF has been signed, the patient will be assigned an enrollment number.

Any SAE that occur after informed consent has been signed must be reported (see Section 7.5.6.1.4).

Data will be collected on medical and surgical history (see Section 7.5.2), prior and concomitant medication (see Section 7.4.8) and demographics (see Section 7.5.4).

Medical examination of current flare (see 7.5.3), local screening laboratory safety assessments (see Section 7.5.6.2), vital signs and physical examination (see Section 7.5.6.3) and a 12-lead ECG (see Section 7.5.6.4) will be performed.

The joint that is most affected, i.e. most painful, will be defined as the index joint and the patient will assess the pain intensity in the index joint on a VAS and Likert scale. These pain assessments will be done as close as possible to randomization and will serve as baseline values.

Once all inclusion and exclusion criteria have been reviewed and recorded (see Section 7.3) and the patient has been found eligible, the patient will be randomized and assigned a randomization number.

Prior to the first IMP administration, blood will be collected for central laboratory safety assessments (see 7.5.6.2), CRP and SAA(see 7.5.5.6), immunogenicity assessments (see 7.5.6.5), exploratory inflammatory biomarkers (see 7.5.8), exploratory pharmacogenetic markers (see 7.5.8.3) and IL-1Ra/anakinra serum concentration assessments (see 7.5.7). The patient assessment of health related quality of life (SF-36® and EQ-5D-5L), the physician's assessment of clinical signs will be performed (see 7.5.5).

Once all predose assessments have been completed, the IMP (i.m. and s.c. injections) will be supervised or administered by the investigator. If the patient or a caregiver is to administer subsequent s.c. injections at home, detailed instructions will be given before discharge (not applicable if patient is hospitalized) (see 7.4.6.3) and IMP for Days 2 and 3 will be provided to the patient.

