7.5.2 Medical and surgical history

The patient's medical and surgical history will be recorded in the eCRF at Visit 1 at first flare and will be updated at Visit 1 of subsequent flares.

The patient's gouty arthritis, the disease duration, the number of gouty arthritis flares during the past 12 months, presence of tophi and presence of gout-related joint damage will be recorded at the first flare.

Detailed information on the presence of the following selected comorbidities will be collected: CKD, current or previous symptoms of heart failure, diabetes, hypertension, obesity, coronary artery disease, hypercholesterolemia, osteoporosis and presence of severe infections. For definitions, see Appendix 3.

Intolerance, unresponsiveness, contraindication or other inappropriateness for treatment with NSAIDs and colchicine will be recorded.

The source of information may be medical records, referral letters, interviews and/or clinical assessments.

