### **11.3 Medical and surgical history and concurrent illnesses**

All medical and surgical history data will be coded using the MedDRA Version 19.1 and the same version will be used throughout the study.

Medical and surgical history at baseline will be presented by SOC and PT for the ITT, PP, and safety populations. Medical and surgical history reported after randomization will be presented separately (see Section 18.6).

Detailed information on the presence of the following selected comorbidities will be presented in a separate table for the ITT, PP, and safety populations: eGFR category, current or previous symptoms of heart failure, diabetes mellitus, hypertension, obesity, cardiovascular disease, hyperlipidemia, cerebrovascular disease and osteoporosis (see Sections **Error! Reference source not found.**, 18.8, 18.9, 18.10 and 18.11).

Data from physical examination will be presented as “normal” or “abnormal” at Day 1 and Day 15 for each flare for the ITT, PP, and safety populations. Any persisting abnormalities should be stated each time the examination is performed in medical history and new abnormalities should be recorded as AEs.

Baseline ECG will be presented for each flare.

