### **18.12 Start of prior and concomitant medication**

If the start or end date of medication is (partly) missing so that categorization in time periods of medication cannot be done, the question regarding if medication was taken prior to the study will be used for the categorization.

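### SAP 18.6 reports undated medical history as starting after randomization, even when it was recorded before randomization and the first dose

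*SAP*

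**What the plan says.** **The rule.** SAP 18.6 consists of one sentence: "If the start date is missing, the medical and surgery history will be reported as started after randomization (first IMP injection"). It has no exception for the visit at which the entry was made, or for an end date that is known.

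**Where it is used.** SAP 11.3 plans two presentations. For the first, "Medical and surgical history at baseline will be presented by SOC and PT for the ITT, PP, and safety populations". For the second, "Medical and surgical history reported after randomization will be presented separately", and that sentence refers to 18.6 for the split.

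**When history is collected.** Protocol 7.5.2 states that history "will be recorded in the eCRF at Visit 1 at first flare and will be updated at Visit 1 of subsequent flares". Protocol 7.5.1.3 (Baseline, Visit 1) lists the step, "Data will be collected on medical and surgical history", ahead of the eligibility review, randomization and first IMP administration.

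**The neighbouring rule for medications.** Where missing dates prevent classification of a medication, SAP 18.12 states that "the question regarding if medication was taken prior to the study will be used for the categorization".

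**The concern.** A missing start date is one unknown; whether the condition preceded treatment is another. For an entry made at the first Visit 1, the second is known: the patient had, or had had, the condition before being randomized. SAP 18.6 sets that knowledge aside and assigns the entry to the one period in which it cannot have started.

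The error runs in one direction only. The baseline history table can lose conditions through this rule but cannot gain any, and the post-randomization table can only gain them. A reader of the study report would see a baseline history that is too short and a list of later history containing conditions that are not new. At stake is the accuracy of two descriptive tables. No treatment comparison depends on them.

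**Working it through.** No figure in the plan is involved, so the check is a reading of the sections against each other.

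1. **Order of events at the first Visit 1.** Protocol 7.5.1.3 puts history collection before randomization, and randomization before the first injection. It must be so, because several exclusion criteria in protocol 7.3.2 (previous malignancy, recent cardiovascular events, substance abuse) cannot be reviewed without the history.

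2. **What 18.6 does to an undated entry from that visit.** The only input to the rule is whether the start date is missing. If it is, the entry is classed as starting after first IMP. Steps 1 and 2 contradict each other for every such entry.

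3. **Known end dates.** Take an operation or a resolved illness with no start date but an end date years before the study. Under 18.6 it is still reported as starting after randomization, so it would start after it ended. The corresponding adverse event rule in SAP 16.2 avoids this: an event of unknown start is taken as treatment emergent unless its end is known to precede first IMP. SAP 18.6 has no such exception.

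4. **The protocol's own test for a pre-existing condition.** Protocol 7.5.6.1.1 identifies one by its presence before adverse event reporting begins and its entry on the pretreatment history or examination form. A start date is not required.

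5. **Partial dates.** SAP 9.1 says that Section 18 deals with partly as well as wholly missing dates. Sections 18.4 and 18.5 do so for the gout diagnosis. Section 18.6 does not say whether a year alone, or a year and month, counts as missing.

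6. **Which outputs are exposed.**
   - *Exposed:* the baseline and post-randomization history presentations of SAP 11.3.
   - *Not exposed:* the selected-comorbidities table, also in SAP 11.3. The references to Section 18 that can be read there are 18.8 to 18.11; one does not resolve, and its place before 18.8 suggests 18.7 (eGFR category). Protocol Appendix 3 and SAP 18.7 to 18.11 define these items by presence, laboratory value, BMI or treatment, not by date of onset.
   - *Not exposed:* the reasons why NSAIDs and colchicine are inappropriate (SAP 11.2), the adverse event tables (SAP 16.2), the per-protocol criteria (SAP 8.2), the primary model and the efficacy subgroups (SAP 14.1 and 14.1.1). None uses a history start date.

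7. **Size.** Neither document reports or predicts how many entries lack a start date. An assumed percentage of undated entries would only return itself as the percentage misplaced, so a range adds nothing. Nor would that percentage carry over to a table row. SAP 9 makes patients the denominator, and a patient whose undated entry is moved stays in the row if another, dated entry has the same term.

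**The case against.** **The default is cautious.** Treating unknown dates as post-treatment is usual for adverse events. That convention guards against missing a drug effect. The history tables serve no such purpose, and moving a known earlier condition out of baseline protects nothing.

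**SAP 11.3 could be read by time of reporting.** Its second presentation concerns history reported after randomization, so one might hold that Visit 1 entries stay at baseline in any case. But the sentence refers to 18.6, and 18.6 classifies by start. If time of reporting already decided the matter, 18.6 would have nothing to do.

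**The medication rule is not a like-for-like precedent.** This stands. SAP 18.12 relies on a question that was collected. No equivalent question is documented for history, so the contrast shows only that the SAP uses other evidence where it has it.

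**The comorbidity profile of the trial is safe.** This also stands. A reader might infer that the rule understates the comorbidity that defines the trial population. The documents do not support that. Inclusion criterion 8 can be met through intolerance or lack of response alone, and the comorbidities that the sponsor singled out, as well as the reasons for unsuitability, have tables of their own.

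**Nothing moves into the safety analysis.** This stands too. A reader might infer that old conditions would be counted as new events on treatment. Adverse events are recorded and tabulated separately, and protocol 7.5.6.1.1 keeps pre-existing conditions out of them unless they worsen or recur more often.

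**Conclusion.** The rule is wrong as written. Any undated entry from the first Visit 1 is placed after an event that it is known to precede, and no other section overrides this. The consequence is minor: one pair of descriptive tables is affected. Undated Visit 1 entries arise before allocation in a double-blind trial, so no systematic difference between arms is expected.

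The direction of the error follows from the text. Its size does not, and cannot be estimated from the documents. It is tempting to say that undated entries are mainly long-standing chronic conditions, or that a substantial share of history is affected. The first is plausible but is inference; the second has no support in either document. If a year alone satisfies 18.6, few entries may be touched.

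The conclusion rests on 18.6 being applied literally and on history being entered in the order that protocol 7.5.1.3 gives.

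**What to change.** Reword SAP 18.6 along these lines:

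- An entry recorded at Visit 1 of the first flare, identified by its visit or date of entry, counts as baseline when its start date is missing or partial, unless the known date parts place it after first IMP.
- An entry whose known end date precedes first IMP counts as baseline, whenever it was recorded.
- An undated entry first added at a later flare, and not covered by the previous point, is shown as *start unknown*. It may be an old condition recalled late, so it should not be reported as starting after randomization.

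The cost is a short change to the SAP and to the programming of two tables, with no effect on any analysis. One point needs checking first. Protocol 7.5.2 says that history is recorded at the first Visit 1 and updated later, but neither document says that the visit or date of entry is kept for each record. Protocol 7.5.6.4 also sends baseline ECG abnormalities to medical history, and SAP 11.3 does the same for persisting examination findings. If the time of entry cannot be retrieved from the eCRF, undated entries that no end date resolves should be shown as *start unknown*.
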